## 2. Incidence of the 90-day endpoint and effects of our interventions

The events included in MAKE-D are death, need for acute dialysis, and persistent decline in kidney function. These events overlap. As previously discussed and summarized in Tables 4 and 5, most published randomized trials that investigated the proposed interventions did not report on these outcomes. However, for those that did track these events, acute dialysis was necessary in 0-7%, death occurred in 0-6%, and persistent decline in kidney function occurred in up to 19% of patients. Using the VA Austin database, we identified 25,909 Veterans who recently underwent coronary or non-coronary angiography who met our study entry criteria. Examining event rates at 90 days following angiography, we found that 1% died, 5% initiated dialysis, and 4% had a persistent increase in SCr of at least 50% (only about one-half of the patients had a measurement of SCr at 90 days). Overall, 8.7% had at least one of these events within 90 days. We therefore believe that the baseline incidence of MAKE-D in this patient population is 8.7%. Assuming an equal distribution of use of NAC versus no use of NAC and saline versus bicarbonate in this population with an overall event rate of 8.7%, a 25% reduction in the incidence of the composite primary outcome with bicarbonate (vs. saline) and with NAC (vs. placebo) would lead to the distribution of events with each treatment combination shown in Model 1. Using this approach, the overall sample size estimate, assuming a type 1 error of 0.025, 90% power, and 3% loss to follow-up, would be 6,500 subjects.

**Model 1**

|         | Bicarbonate | Saline |      |
|---------|-------------|--------|------|
| NAC     | 6.4%        | 8.5%   | 7.5% |
| Placebo | 8.5%        | 11.3%  | 9.9% |
|         | 7.5%        | 9.9%   |      |

Overall event rate  
**8.7%**

Our proposed sample size of 7,680 patients, based on the rates summarized in Model 2 (see below), arises from more conservative assumptions. The 8.7% overall event rate derived from the VA Austin database represents the incidence of this composite outcome in a patient population in which the specific use of preventive care for CIAKI is unknown. Recognizing that these patients may or may not have received the interventions we propose to study, we have taken a more conservative approach to estimating the necessary sample size by assuming that this 8.7% event rate represents the rate in each of the control arms (i.e., placebo with saline or bicarbonate and saline with or without NAC) as shown in Model 2. In this proposed model, the overall event rate in the entire population is 7.6%, which is 13% lower than the event rate (8.7%) which is suggested by our analyses of the VA Austin database. Using this more conservative estimate of the overall event rate resulted in our proposed sample size of 7,680 patients. We believe that this approach will help ensure that our study is not underpowered and is grounded on conservative, yet clinically reasonable event rate estimates.

**Model 2**

|         | Bicarbonate | Saline |       |  |
|---------|-------------|--------|-------|--|
| NAC     | 5.59%       | 7.46%  | 6.52% | } Overall event rate
7.6% |
| Placebo | 7.46%       | 9.95%  | 8.70% |  |
|         | 6.52%       | 8.70%  |       |  |

Most trials have reported effect sizes for the outcome of CIAKI rather than for our defined 90 day primary composite outcome. For CIAKI, a recent meta-analysis reported a pooled relative risk of 0.62 (95% CI: 0.45-0.86) favoring bicarbonate when compared to saline, with the individual study effect sizes ranging from 2% to 92%. There were too few studies that systematically tracked other clinical outcomes to reliably analyze the risks for dialysis (RR=0.51, 95% CI: 0.17-1.51) or death (RR=0.83, 95% CI: 0.32-2.19). Similar results have been reported for NAC. The Planning Committee felt that a 25% effect size would be clinically meaningful and within the range of what might be expected from previous studies, since the reduction in 90 day clinical outcomes is likely mediated by a reduction in CIAKI, which available literature suggests is reduced by as much as 92%.

Therefore, considering Model 2, we postulate that:

- Under control conditions, the 90-day event rate for our primary outcome (MAKE-D) is 8.7%
- Each of the two interventions will prevent 25% of these events
- Under each intervention condition, the 90-day event rate is 6.52%
- The absolute effect of each intervention will be a 2.18% reduction in 90-day events

We have two primary hypotheses, one for each main effect in the model. We will therefore allocate the type I error of 5% equally across the two interventions, assigning a type I error of 2.5% to each. Including a third test for the interaction term from the set of primary hypotheses would slightly decrease the statistical power. We discuss the potential impact of the interaction on the power of the study later in this section. One interim analysis using an O’Brien-Fleming rule will be carried out when half the expected number of MAKE-D events have occurred.

## **B. Primary end-points**

The two main interventions will be analyzed in the same way. Hence, we fully describe the bicarbonate versus saline intervention and the MAKE-D outcome. The analyses for the other intervention, NAC versus placebo, are analogous.

The null hypothesis is that the two treatment groups (bicarbonate and saline) do not differ in terms of the proportion of subjects who experience MAKE-D events. The alternative hypothesis is that the absolute difference in the incidence of MAKE-D between the bicarbonate intervention group and the saline group is 2.18% or more.

### Formal statement of the null hypothesis

Under the null hypothesis:

- The proportion of 90-day MAKE-D events for patients administered bicarbonate is 8.70%
- Under the alternative hypothesis, the proportion of 90-day MAKE-D events for patients administered saline is 8.70%

The formal hypothesis test is two-sided allowing for bicarbonate to be either more or less effective than saline. However, the study of bicarbonate will only be viewed as more successful if subjects treated with bicarbonate have a significantly lower proportion of 90-day MAKE-D events than patients who receive saline. We will test this hypothesis using the strategy described in section A.

### **C. Secondary end-points**

Our secondary objectives, as previously outlined, will be tested using a logistic regression analysis similar to the primary objective. These objectives are:

1. To assess the effectiveness of the interventions to prevent CIAKI, defined by an increase in SCr of  $\geq 0.5$  mg/dL and/or  $\geq 25\%$  at 96 hrs following angiography compared to baseline values.
2. To assess the effectiveness of the interventions for the prevention of the following outcomes within 90 days of coronary or non-coronary angiography:
  - a) death
  - b) major adverse kidney endpoints (MAKE) including need for acute dialysis or persistent decline in kidney function defined by an increase in SCr of at least 50% at 90 days
  - c) hospitalization with acute coronary syndrome, heart failure, or cerebrovascular accident defined by primary or secondary ICD-9 discharge diagnosis codes of acute coronary syndrome (i.e., STEMI, NSTEMI, unstable angina), heart failure, or cerebrovascular accident and/or by documentation of any of these three events in the hospital discharge summary.
  - d) all-cause hospitalization

### **D. Tertiary (exploratory) end-points**

We also wish to explore whether the interventions prevent adverse outcomes occurring within the first year after angiography. To that end, using logistic regression analysis, we will determine whether the interventions prevent:

1. Development of end-stage renal disease within one year following angiography defined by the requirement for chronic dialysis for  $\geq 3$  months based on documentation in the United States Renal Data System
2. Death within one year following angiography based on documentation in the VA Beneficiary Identification and Records Locator System, the National Center for Health Statistics National Death Index database, or the Social Security Administration’s Death Master File

#### **E. Additional exploratory analyses**

We will explore several other hypotheses related to the binary 90 day MAKE-D outcome:

1. The combination of bicarbonate and NAC (interaction term) is more effective than bicarbonate or NAC alone.
2. (Per Protocol analysis) Bicarbonate, NAC, and their combination reduce the incidence of the primary outcome, MAKE-D, among subjects who received the full dose of bicarbonate.
3. (Per Protocol analysis) Bicarbonate, NAC, and their combination reduce the incidence of the primary outcome, MAKE-D, among subjects who received the full course of NAC.
4. Bicarbonate, NAC, and their combination reduce the incidence of the individual components of MAKE-D, each treated as a separate outcome: death, need for acute dialysis, and persistent decline in kidney function.
5. Bicarbonate, NAC, and their combination reduce the incidence of each of the individual cardiovascular components of the secondary outcome; namely acute coronary syndrome, heart failure, and cerebrovascular accident.
6. Bicarbonate, NAC, and their combination result in a greater reduction in the incidence of MAKE-D outcomes in subjects who develop CIAKI compared to those who do not develop CIAKI.
7. Bicarbonate, NAC, and their combination increase the mean number of days that participants are alive and hospitalization free (hospital free days) in the 90 days after angiography.

8. The benefits of bicarbonate, NAC, and their combination on MAKE-D outcomes are independent of the volume and rate of fluid administration above the minimum values prescribed in the protocol.

This brief list entails a large number of analyses. However, the sample size is large and the implicit hypotheses are highly inter-correlated. Thus, we anticipate that we can use a significance level of 1% ( $p = 0.01$ ) to detect associations of potential clinical importance in these exploratory analyses.

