## XVII. BIOSTATISTICAL CONSIDERATIONS

### A. Overview of design

#### 1. The analytic model

There are two primary hypotheses that will be tested: 1) peri-procedure infusion of sodium bicarbonate is superior to infusion of sodium chloride for the prevention of serious, adverse clinical events within 90 day of angiography and; 2) peri-procedure administration of oral N-acetylcysteine (NAC) is superior to placebo for the prevention of serious, adverse clinical events within 90 day of angiography. The study will enroll 7,680 subjects over 2.5 years and evaluate each subject 90 days after the intervention. Within each site, subjects will be randomly assigned to one of four combinations of study interventions: 1) bicarbonate and NAC placebo, 2) saline and NAC placebo, 3) bicarbonate and NAC and 4) saline and NAC.

The study design for the primary hypothesis is a 2 x 2 factorial design with a binary outcome - any of a selected list of important clinical events occurring within 90 days of study treatment including death, need for acute dialysis, and persistent change in SCr at 90 days of at least 50% from the baseline SCr. We denote the 90-day binary outcome as ‘MAKE-D’ (major adverse kidney events and death). The binary predictors are the interventions bicarbonate and NAC. The interaction term, bicarbonate\*NAC, represents the combination of these two interventions. The primary analysis starts with a logistic regression analysis with three binary predictors.

For the primary hypothesis, the model equation for the analysis is:

$$\text{MAKE-D} = \beta_1 * \text{Bicarbonate} + \beta_2 * \text{NAC} + \beta_{12} * \text{Bicarbonate} * \text{NAC} \quad \textbf{Model Equation}$$

where,  $\beta_1$ ,  $\beta_2$ , and  $\beta_{12}$  are the logistic regression beta coefficients.

The two main questions of interest that we will test for the primary hypothesis are:

- 1) Does bicarbonate reduce the incidence of MAKE-D?
- 2) Does NAC reduce the incidence of MAKE-D?

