#### Impact of Potential Interaction between Treatments on Sample Size and Statistical Power

The prior discussion of sample size and statistical power is predicated on the assumption that the effects of bicarbonate and NAC are independent. Stated in other terms, we have assumed that the relative reduction in the rate of MAKE-D events in patients assigned to bicarbonate/NAC compared to saline/NAC will be the same as that in patients assigned to bicarbonate/placebo compared to saline/placebo. Similarly, we have assumed that the relative reduction in the rate of MAKE-D events in patients assigned to bicarbonate/NAC compared to bicarbonate/placebo will be the same as that in patients assigned to saline/NAC compared to saline/placebo. The event rates under these assumptions are summarized in the following model.

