**Model 2 in the Absence of Interaction**

|         | Bicarbonate | Saline |       |
|---------|-------------|--------|-------|
| NAC     | 5.59%       | 7.46%  | 6.52% |
| Placebo | 7.46%       | 9.95%  | 8.70% |
|         | 6.52%       | 8.70%  |       |

The rate of 5.59% for the combination of bicarbonate and NAC is lower than the rate of 7.46% for NAC with saline because, some patients who do not respond to NAC will, at random, respond to bicarbonate. This is what is meant by ‘the absence of interaction.’ In contrast, an interaction between NAC and bicarbonate could result in an absence of further benefit from combined treatment as compared to treatment with either agent alone.

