5.3.1. Testing for Interaction

A multivariable logistic regression model to be fitted includes two binary predictors with an interaction term, and can be expressed as:

$$\text{Log (Odds (MAKE-D))} = \alpha + \beta_1 X_1 + \beta_2 X_2 + \beta_3 X_1X_2 \quad (\text{Model 1})$$

Where X_1 is the indicator for IV intervention (1=Bicarb, 0=Saline), X_2 is the indicator variable for oral intervention (1=NAC, 0=Placebo), and X_1X_2 is the interaction of the two interventions (1=Bicarb and NAC, 0=otherwise).

The parameter β_1 will estimate the independent effect of Bicarb compared to Saline, the parameter β_2 will estimate the independent effect of NAC compared to Placebo, and the parameter β_3 will estimate the additional effect of both Bicarb and NAC.

Presence of significant interaction between Bicarb and NAC (either beneficial or detrimental) will be tested as follows.

Null	$H_0: \beta_3 = 0$
Alternative	$H_a: \beta_3 \neq 0$

If the Wald Chi-square test has $p > 0.05$, then the null hypothesis for interaction cannot be rejected and we will conclude that there is no evidence of significant modification of effect from receiving both Bicarb and NAC.

If the Wald Chi-square test has $p \leq 0.05$, then the null hypothesis for interaction will be rejected and alternative hypothesis accepted to conclude that a significant modification of

effect exists from receiving both Bicarb and NAC. Primary analysis will proceed as described in section 5.3.3.

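### The exploratory hypothesis that the combination beats either agent alone is tied to the interaction term, which is about zero in the plan's own base case, where that hypothesis is true

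*Protocol*

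**What the plan says.** Protocol XVII.E lists eight exploratory hypotheses on 90-day MAKE-D, to be judged at the 1% level. The first is: "The combination of bicarbonate and NAC (interaction term) is more effective than bicarbonate or NAC alone". The parenthesis is the only indication of how it is to be tested. Protocol XVII.A.1 says that the product term "represents the combination of these two interventions". SAP 5.3.1 fits Model 1 with b1 (bicarbonate), b2 (NAC) and b3 (product), and says that b3 "will estimate the additional effect of both Bicarb and NAC". It describes b1 and b2 in that model as independent effects.

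Protocol XVII.F uses interaction in the standard sense. It sizes the trial on equal relative effects: "we have assumed that the relative reduction in the rate of MAKE-D events in patients assigned to bicarbonate/NAC compared to saline/NAC" is taken to be the same as that between bicarbonate and saline under placebo. Under the heading for no interaction it adds: "The rate of 5.59% for the combination of bicarbonate and NAC is lower than the rate of 7.46% for NAC with saline".

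SAP 5.3.3 fits bicarbonate v saline within NAC (Model 3) and NAC v placebo within bicarbonate (Model 5), but only if the interaction has p ≤ 0.05. The SAP does not carry item 1 forward as a separate analysis.

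**The concern.** Item 1 asks a question about cells: is the event rate in Group 1 (both agents) lower than in Group 3 (bicarbonate alone) and in Group 2 (NAC alone)? The test it names asks whether the effect of one agent differs, on the odds-ratio scale, by level of the other. These are different questions. XVII.F itself gives a set of rates in which the first answer is yes and the second is no, and that set is the design's base case.

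At stake is the answer to one exploratory question. If item 1 is analysed as labelled, its statistic is null when the two agents work independently as assumed, and it points the wrong way when they partly overlap.

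**Working it through.** **Inputs.** Cell rates from Protocol XVII.F, Model 2 without interaction (columns bicarbonate, saline, margin): "NAC | 5.59% | 7.46% | 6.52" and "Placebo | 7.46% | 9.95% | 8.70". Attenuated rates for the combination come from Table 11. There are 1,920 patients per cell and 3% loss, so 1,920 × 0.97 = 1,862 evaluable per cell. The exploratory level is 1%, taken as two-sided.

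**Reproducing the plan first.** Margins: (5.59 + 7.46)/2 = 6.525% and (7.46 + 9.95)/2 = 8.705%, matching 6.52% and 8.70%. The two-proportion formula (pooled variance under the null) for 8.70% v 6.52%, two-sided alpha 0.025 and 90% power gives 3,671 per arm, or 7,342. The plan states 7,450 after its O'Brien-Fleming adjustment, and 7,450/0.97 = 7,680. With 3,725 per margin the power values are 90.5%, 87.2%, 83.6%, 79.1% and 69.3%, matching Table 11. The plan states no power for item 1.

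**Interaction in the base case.** On the relative-risk scale, the ratio of risk ratios is (5.59 × 9.95)/(7.46 × 7.46) = 0.9994. On the fitted scale:

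b3 = logit(0.0559) − 2·logit(0.0746) + logit(0.0995) = −2.8267 + 5.0362 − 2.2028 = +0.007 (odds ratio 1.007).

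Each cell contributes 1/[n·p·(1−p)] to the variance, so SE = √(0.01018 + 0.00778 + 0.00778 + 0.00599) = 0.178. The test rejects in favour of the combination 0.4% of the time at the 1% level and 2.3% at 5%, which is only its type I error.

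**The contrast item 1 describes.** Combination v one agent alone is b1+b3 or b2+b3. In the base case each is logit(0.0559) − logit(0.0746) = −0.309 (odds ratio 0.73), with SE = √(0.01018 + 0.00778) = 0.134 and |z| = 2.30.

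**Under the plan's attenuation scenarios** (other cells unchanged):

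| Attenuation | Combination | One agent | b3 | Odds ratio, combination v one agent |
|---|---|---|---|---|
| none | 5.59% | 7.46% | +0.007 | 0.73 |
| 10% | 5.78% | 7.46% | +0.042 | 0.76 |
| 30% | 6.15% | 7.46% | +0.108 | 0.81 |
| 50% | 6.53% | 7.46% | +0.172 | 0.87 |

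In every row the combination is the best cell and b3 is zero or positive, that is, null or pointing against it.

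**Access to Models 3 and 5.** In the base case the interaction reaches p ≤ 0.05 about 5% of the time (2.3% + 2.7%), so these comparisons would seldom be fitted.

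**Power of the direct contrasts**, 1,862 per cell. The two contrasts share Group 1, so they are correlated (0.57 in the base case):

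| Scenario | One, 1% | Both, 1% | One, 5% | Both, 5% |
|---|---|---|---|---|
| Base case | 39% | 24% | 63% | 49% |
| 50% attenuation | 7% | 2% | 20% | 9% |

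These are normal approximations. Simulation agrees to about one percentage point.

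**The case against.** **It may mean synergy.** The parenthesis suggests that item 1 asks whether the joint effect exceeds the product of the two, for which b3 is the right test. That reading is possible, but then the sentence is wrong, because beating each agent alone is not synergy. The text needs changing on either reading.

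**The supporting wording is defensible.** As a variable, the product term does flag patients on both agents, and b3 can fairly be called an effect beyond b1 + b2. Calling b1 and b2 of Model 1 independent effects is loose, since each applies only at the control level of the other factor. But no test uses them: the main effects are tested in Model 2, where the label fits. This all stands, so only item 1 is wrong as written.

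**The contrasts are already there.** Models 3 and 5 are Group 1 v Group 2 and Group 1 v Group 3. That is true, but they depend on the one result that is not expected when the agents act independently.

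**A stronger inference fails.** A reader might infer that the trial would report the combination as no better, or reach a wrong conclusion about treatment. The documents do not support this. SAP 5.3.1 reads a non-significant interaction as no evidence of effect modification, which is correct, and XVII.F says openly that the combination does better without interaction. Conclusions rest on the two main effects. Even at 50% attenuation b3 is about one standard error (0.172/0.174) and would be significantly unfavourable only about 6% of the time at 1% and 17% at 5%.

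**Conclusion.** The point holds for one exploratory analysis. The test named for item 1 does not address item 1: its expected value is about zero when the hypothesis is true in the base case, and it moves against the combination under partial attenuation while the combination is still the best cell. The two primary tests, the sample size and the main-effect conclusions are unaffected.

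The b3 values and odds ratios depend only on the plan's cell rates. The standard errors and power figures also assume 1,862 evaluable patients per cell and two-sided testing. The value is exactly null, up to rounding, on the relative-risk scale on which the plan defines no interaction, and +0.007 on the logit scale that it fits.

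**What to change.** 1. In Protocol XVII.E item 1, remove the reference to the interaction term. Test b1+b3 (Group 1 v Group 2, NAC alone) and b2+b3 (Group 1 v Group 3, bicarbonate alone) from Model 1, whatever the interaction p-value. Claim that the combination beats either agent alone only if both favour it at the 1% exploratory level.
2. Add the same analysis to the SAP. Keep b3 solely as the test of effect modification. If synergy was meant, reword item 1 to say so and leave b3 as its test.
3. In SAP 5.3.1, label b1 and b2 of Model 1 as the bicarbonate effect under placebo and the NAC effect under saline.
4. State the power of the two-contrast rule with the analysis: about 24% at 1% in the base case and about 2% at 50% attenuation. Say that a null result is not evidence of no added benefit. For scale, 80% power on a single contrast at 1% would need about 4,073 patients per cell against 1,920 planned, so report estimates with confidence intervals.

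The cost is a few sentences and two ESTIMATE statements on a model already fitted, with no extra patients or data. The downside is that the replacement, though it asks the right question, will usually be inconclusive at this sample size.

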3.4. Definition of per-Protocol sample

Adherence to allocated intervention according to the protocol, as outlined in Table 3, will be ascertained for randomized subjects for identification of “per-Protocol” sub-group. Percent adherence will be determined for IV fluid and oral interventions separately.

Oral medication adherence will be computed by capsule count only as follows:

$$\% \text{ adherence} = \frac{\text{Total\#capsulesTaken}}{40} \times 100\%$$

Those who had (>=80% and <=120%) adherence by the capsule count will be considered as adherent to the protocol.

IV fluid adherence will be based on the recommended ranges for each period (pre-procedure, intra-procedure, and post-procedure) described in Table 3.

Pre – procedure: Volume of 3 to 12 ml/kg

Intra – procedure: Rate of 1 to 1.5 ml/kg/hour

Post – procedure: Volume of 6 to 12 ml/kg

% adherence will be computed as a range from % of lower limit to % of upper limit outlined in Table 4.

Table 4. IV fluid adherence table

Pre-Procedure		Intra-procedure		Post-procedure	
Volume (mL/kg)	% Dose Given	Rate (mL/kg/Hr)	% Dose Given	Volume (ml/kg)	% Dose Given
1	33.3%	0.5	50%	1	16.7%
2	66.7%	0.6	60%	2	33.3%
3	100%	0.7	70%	3	50%
4	100%	0.8	80%	4	66.7%
5	100%	0.9	90%	5	83.3%
6	100%	1.0	100%	6	100%
7	100%	1.1	100%	7	100%
8	100%	1.2	100%	8	100%
9	100%	1.3	100%	9	100%
10	100%	1.4	100%	10	100%
11	100%	1.5	100%	11	100%

12	100%	1.6	106.7%	12	100%
13	108.3%	1.7	113.3%	13	108.3%
14	116.7%	1.8	120%	14	116.7%
15	125%	1.9	126.7%	15	125%

Those who had (>=80% and <=120%) adherence for, at minimum, the pre-procedure and intra procedure periods will be considered as adherent to the protocol.

Those who are adherent to the protocol for both oral study medication and IV study fluid will be included in the “per-Protocol” analytic sub-sample.

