5.3.5. Sensitivity Analysis

We will refit Models 1 and 2 to evaluate the odds of the event of interest at 90 days post angioplasty among those allocated to IV isotonic sodium bicarbonate therapy compared to those allocated to IV isotonic saline, and among those allocated to NAC compared to those allocated to Placebo. The primary analysis will be repeated under 5 different scenarios as follows and the results will be displayed in a Forest plot.

(1) On the first “per-Protocol” sample with 80-120% adherence as defined in **3.4** to evaluate efficacy among those adherent to the protocol. Subjects who are over-adherent ($\geq 120\%$) or have had a non-protocol administration of study medication, particularly IV sodium bicarbonate, will be excluded.

(2) On the second “per-Protocol” sample with $\geq 80\%$ adherence as defined in **3.4** including those subjects who are over-adherent or have had a non-protocol administration of study medication, particularly IV sodium bicarbonate.

(3) On the “ITT” cohort that includes those with the initial 90-day blood sample but are missing the confirmatory sample.

(4) On the “ITT” cohort assuming all those with missing endpoint data had events before 90 days (the worst case scenario), and

(5) On the “ITT” cohort assuming all those with missing endpoint data had no events before 90 days (the best case scenario)

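### Protocol and SAP define different per-protocol sets: the protocol's literal wording omits the matching comparator, and the SAP's joint rule drops patients from the fluid comparison for missed capsules

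*Protocol*

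**What the plan says.** **Protocol XVII.E (Additional exploratory analyses), items 2 and 3.** Both are labelled per-protocol. Item 2 asks whether bicarbonate, NAC and their combination "reduce the incidence of the primary outcome, MAKE-D, among subjects who received the full dose of bicarbonate". Item 3 asks the same "among subjects who received the full course of NAC". The protocol does not define full, gives no matching condition for saline or placebo, and sets a 1% significance level for this group of analyses.

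**SAP 3.4.** Adherence to the allocated product, active or control, is calculated separately for fluid and capsules:

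- Capsules: number taken divided by 40. Patients with 80% to 120% "adherence by the capsule count will be considered as adherent to the protocol".
- Fluid: 80% to 120%, required at least for the pre- and intra-procedure periods.

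The two are then combined: "Those who are adherent to the protocol for both oral study medication and IV study fluid will be included" in the per-protocol sub-sample.

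**SAP 5.3.5.** Models 1 and 2, which cover both treatment comparisons, are refitted on the "sample with 80-120% adherence as defined in" section 3.4, and again on a second version at 80% or more with no upper limit. These are two of five sensitivity scenarios. No separate significance level is given.

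The SAP's list of revisions changes how adherence is calculated but does not mention the protocol's two sets.

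**The concern.** There are two separate problems.

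First, the protocol's sets are defined by receipt of the active agent. A set made up of bicarbonate recipients has nobody on saline to compare them with, and a set of NAC recipients has nobody on placebo. Neither item can answer the question it leads with.

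Second, the SAP's sets have both controls but tie each comparison to adherence with the other treatment. Study fluid is finished within hours of the procedure, whereas capsules run to day 4. Under the joint rule, a patient's place in the fluid comparison depends on days of later capsule-taking. That loses patients who received exactly the fluid they were assigned, and it removes some early primary events for a reason that has nothing to do with the fluid.

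Because the documents differ, the same patient can be in one per-protocol set and out of the other. The per-protocol results will sit in the same forest plot as the other sensitivity analyses, so one agreed definition should be on file before the data are seen.

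**Working it through.** **1. Who is in each set**

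| Patient | Protocol item 2 | Protocol item 3 | SAP joint set |
|---|---|---|---|
| Bicarbonate, full fluid, 30 of 40 capsules (75%) | in | out | out |
| Saline, full fluid, all capsules | out (no bicarbonate) | in only if capsules were NAC | in |
| NAC, full fluid, 32 of 40 capsules (80%) | in only if fluid was bicarbonate | not a full course on a strict reading | in |
| Placebo, full fluid, all capsules | in only if fluid was bicarbonate | out (no NAC) | in |

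Item 2 keeps only the two bicarbonate cells of the factorial, so NAC v placebo can be estimated there but bicarbonate v saline cannot. Item 3 keeps only the two NAC cells, so the reverse holds.

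**2. The 40-capsule denominator (SAP Table 3)**

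There are two doses of 4 capsules on the procedure day and two doses of 4 on each of days 1 to 4: 8 + 4 × 8 = 40. This reproduces the SAP's denominator.

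**3. When 80% can first be reached**

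0.80 × 40 = 32 capsules. The largest possible cumulative counts are:

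- procedure day: 8 (20%)
- day 1: 16 (40%)
- day 2: 24 (60%)
- day 3: 32 (80%)

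The formula makes no allowance for death. A patient who received all the study fluid and died on day 2 has at most 24 of 40, or 60%, and is excluded from both SAP versions. Death within 90 days is a component of the primary endpoint (SAP 3.5.1).

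**4. How many early deaths this could involve**

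The documents give no figure for deaths before day 3. Protocol XVII.A.2 reports that 1% of the historical VA cohort died by day 90. Applied to 7,680 patients this is 0.01 × 7,680 ≈ 77 deaths over the whole 90 days. Deaths before day 3 would be some fraction of that. The planned total of primary events is 0.076 × 7,680 ≈ 584.

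**5. Loss of precision for bicarbonate v saline**

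Let *a* be the proportion adherent to fluid and *b* the proportion adherent to capsules. Assume the two are independent and that event rates are unchanged by the selection. Neither *a* nor *b* is in the documents. The fluid-only set keeps a share *a* and the joint set keeps *a × b*. The ratio of standard errors, joint to fluid-only, is √(a / (a × b)) = 1/√b.

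| Assumed *b* | 1/√b | Rise in standard error |
|---|---|---|
| 0.85 | 1.085 | 8.5% |
| 0.75 | 1.155 | 15% |

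The same formula applies to NAC v placebo, with fluid adherence in place of *b*.

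**The case against.** **The protocol wording may be loose drafting.** Each item asks about bicarbonate, NAC and their combination, which a bicarbonate-only set could not answer, so adherence to the assigned product may have been meant. This is plausible, but the protocol does not say so. A reader might infer that the trial will produce no per-protocol estimate of either effect. The documents do not support that: SAP 3.4 counts adherence to whichever product was allocated, and 5.3.5 refits both comparisons with both controls present.

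**A joint set is an ordinary meaning of per-protocol.** This stands. SAP 5.3.5 refits Model 1, with its interaction term, and that model is best served by a set in which all four cells took what they were assigned. A reader might infer that the joint set is an error. It is not. The narrower point is that it is the only kind of set planned, and it is also used for each factor on its own.

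**Selection is asserted, not measured.** This stands in part. If capsule-taking does not differ between fluid arms, excluding on it need not unbalance them, and the documents give no basis for quantifying a bias. A fluid-adherent set also conditions on something that happens after randomisation. What can be shown from the dosing schedule is that early deaths are excluded mechanically.

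**Size.** A reader might turn the lost patients into a power shortfall. Protocol XVII.A.1 says the exploratory analyses have no power calculation, XVII.E sets 1% rather than 2.5% for them, and any adherence rate is assumed. Protocol XVII.H also expects few dropouts or crossovers because treatment is short, although that is not a capsule-adherence figure. A power claim is therefore not supported.

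**Conclusion.** The point holds, at minor severity. The two documents define different per-protocol sets and nothing reconciles them. The protocol's literal wording leaves out the comparator for the effect each set is named after. The SAP's joint rule keeps the comparators but excludes patients from bicarbonate v saline for missed capsules, including any who received all the fluid and died before day 3.

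The exclusion of early deaths follows from the dosing schedule and the fixed denominator of 40, and needs no assumption. The number affected is not in the documents and is likely to be small. The loss of precision, about 8.5% to 15% in standard error, is illustrative only: it assumes 85% or 75% capsule adherence, independent of fluid adherence.

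The analyses affected are exploratory in the protocol and sensitivity analyses in the SAP. The primary intention-to-treat analysis, sample size and alpha do not change.

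**What to change.** - **Protocol XVII.E.** In item 2, change the set-defining reference to bicarbonate to *assigned study IV fluid*. In item 3, change the set-defining reference to NAC to *assigned capsules*. Cross-refer both to SAP 3.4 so that the numeric adherence limits apply.
- **SAP 5.3.5.** Add factor-specific per-protocol sets: patients adherent to the assigned fluid for bicarbonate v saline, and patients adherent to the assigned capsules for NAC v placebo. Keep the joint set for the interaction or four-cell model.
- **Reporting.** A capsule-adherent set will still exclude deaths before day 3 from NAC v placebo, because the denominator stays at 40. State this where that result is reported.

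The cost is a few words in the protocol, a short addition to the SAP and two analysis flags. SAP 3.4 already calculates the fluid and capsule percentages separately, so no new data are needed and no treatment rule changes.
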